13.7. Analysis of Exploratory Endpoint

Exploratory analyses of RNA expression levels of relevant genes in the *TP53* pathway that may predict response to therapy will be performed on pre- and post-treatment bone marrow biopsies. An optional post-treatment bone marrow biopsy will be pre Cycle 2 Day 1. An estimated 75% of subjects are expected to consent to this optional post-treatment bone marrow biopsy; thus we expect 19-30 of the planned 25-40 subjects to provide an additional biopsy. These exploratory analyses will potentially guide future studies with larger cohorts of patients.

15. APPENDICES

15.1. APPENDIX A: PERFORMANCE STATUS CRITERIA

ECOG Performance Status Scale		Karnofsky Performance Scale	
Grade	Descriptions	Percent	Description
0	Normal activity. Fully active, able to carry on all pre-disease performance without restriction.	100	Normal, no complaints, no evidence of disease.
		90	Able to carry on normal activity; minor signs or symptoms of disease.
1	Symptoms, but ambulatory. Restricted in physically strenuous activity, but ambulatory and able to carry out work of a light or sedentary nature (e.g., light housework, office work).	80	Normal activity with effort; some signs or symptoms of disease.
		70	Cares for self, unable to carry on normal activity or to do active work.
2	In bed < 50% of the time. Ambulatory and capable of all self-care, but unable to carry out any work activities. Up and about more than 50% of waking hours.	60	Requires occasional assistance, but is able to care for most of his/her needs.
		50	Requires considerable assistance and frequent medical care.
3	In bed > 50% of the time. Capable of only limited self-care, confined to bed or chair more than 50% of waking hours.	40	Disabled, requires special care and assistance.
		30	Severely disabled, hospitalization indicated. Death not imminent.
4	100% bedridden. Completely disabled. Cannot carry on any self-care. Totally confined to bed or chair.	20	Very sick, hospitalization indicated. Death not imminent.
		10	Moribund, fatal processes progressing rapidly.
5	Dead.	0	Dead.

15.4. APPENDIX C: Drug-Induced Liver Injury (DILI) Reporting & Additional Assessments

Reporting

To facilitate appropriate monitoring for signals of drug-induced liver injury (DILI), cases of concurrent AST or ALT and TBL and/or INR elevation according to the criteria specified in Section 6.1 require the following:

The event is to be reported to CTEP as a serious adverse event within 24 hours of discovery or notification of the event (*i.e.*, before additional etiologic investigations have been concluded). The appropriate CRF (*e.g.*, Adverse Event CRF) that captures information necessary to facilitate the evaluation of treatment-emergent liver abnormalities is to be completed and sent to CTEP. Other events of hepatotoxicity and potential DILI are to be reported as serious adverse events if they meet the criteria for a serious adverse event defined in Section 7.

Additional Clinical Assessments and Observation

All subjects in whom investigational product(s) or protocol-required therapies is/are withheld (either permanently or conditionally) due to potential DILI as specified in Section 6.1 or who experience AST or ALT elevations $\geq 3 \times$ ULN are to undergo a period of “close observation” until abnormalities return to normal or to the subject’s baseline levels. Assessments that are to be performed during this period include:

Repeat AST, ALT, ALP, bilirubin (total and direct), and INR within 24 hours
In cases of TBL $> 2 \times$ ULN or INR > 1.5 , retesting of liver tests, BIL (total and direct), and INR is to be performed every 24 hours until laboratory abnormalities improve.

Testing frequency of the above laboratory tests may decrease if the abnormalities stabilize or the investigational product(s) or protocol-required therapies has/have been discontinued AND the subject is asymptomatic.

Initiate investigation of alternative causes for elevated AST or ALT and/or elevated TBL:
Obtain complete blood count (CBC) with differential to assess for eosinophilia
Obtain serum total immunoglobulin IgG, Anti-nuclear antibody (ANA), Anti Smooth Muscle Antibody, and Liver Kidney Microsomal antibody 1 (LKM1) to assess for autoimmune hepatitis
Obtain serum acetaminophen (paracetamol) levels
Obtain a more detailed history of:
Prior and/or concurrent diseases or illness
Exposure to environmental and/or industrial chemical agents
Symptoms (if applicable) including right upper quadrant pain, hypersensitivity-type reactions, fatigue, nausea, vomiting and fever
Prior and/or concurrent use of alcohol, recreational drugs and special diets
Concomitant use of medications (including non-prescription medicines and herbal and dietary supplements), plants, and mushrooms
Obtain viral serologies

Obtain CPK, haptoglobin, LDH, and peripheral blood smear

Perform appropriate liver imaging if clinically indicated

Obtain appropriate blood sampling for pharmacokinetic analysis if this has not already been collected

Obtain hepatology consult (liver biopsy may be considered in consultation with an hepatologist)

Follow the subject and the laboratory tests (ALT, AST, TBL, INR) until all laboratory abnormalities return to baseline or normal. The “close observation period” is to continue for a minimum of 4 weeks after discontinuation of all investigational product(s) and protocol-required therapies.

The potential DILI event and additional information such as medical history, concomitant medications and laboratory results must be captured in corresponding CRFs.

15.5. APPENDIX D: CASE REPORT FORM FOR TP53 NGS ASSAY

Clinical Study: _____
Report Date: _____

TUMOR SPECIMEN REPORT

The OCAv3 next-generation sequencing (NGS) assay as employed for KRT-232 (AMG 232) TP53 detection is intended to provide information about mutation or lack of mutation within the TP53 DNA of the patient's tumor. Mutations determined by comparison to the Human Reference Genome hg19 are categorized as single nucleotide variants (SNVs) or insertions/deletions (indels). **NOTE: This report does not indicate potential treatment assignment.**

Patient Initials (First, Last):	Patient Identifier:	MoCha Sample ID:	Gender:
Referring Physician:		Fax:	Tel:
Biopsy Site:	Date Collected:	Primary Diagnosis:	Tumor Content (%):

Mutation(s) Detected: None identified (Delete this text if variants are reported)				
Chromosome:Position	Nucleotide Change	Protein Change	VAF ²	Mutation Type ³
¹ Tumor content was provided by site/address. Reported assay characteristics cannot be guaranteed for specimens that present a tumor content below 20%.				
² Analytical sensitivity is ≥5%				
³ Single nucleotide variant (SNV) or insertion/deletion (INDEL)				
Comments:				
SIGNATURE APPROVAL:				
The signature below attests that the signee has reviewed the data and results reported and concurs with the stated conclusions.				

DISCLAIMER: This assay is considered a Laboratory Developed Test (LDT). Its performance characteristics have been determined through extensive testing although it has not been cleared by the US Food and Drug Administration and such approval is not required for clinical implementation. Furthermore, any Comments included in this report are strictly interpretive and the opinion of the reviewer. This laboratory is certified under the Clinical Laboratory Improvement Amendments (CLIA) for the performance of high-complexity molecular testing for clinical purposes.

Sequencing Assay Information

Methodology, Scope, and Application: The sequencing test utilizes the Thermo Fisher Scientific Oncomine® Comprehensive Assay v3.0 (OCAv3), a next-generation sequencing (NGS) assay that utilizes a multiplex polymerase chain reaction (PCR) with DNA extracted from formalin-fixed tissue for sequencing on the Ion S5 XL platform and analyzed by Torrent Suite Software v5.2 and Torrent Variant Caller v5.2. The OCAv3 NGS Assay can reliably identify the presence or absence of mutations and polymorphisms within the TP53 gene, with results compared to the TP53 sequence (NM_000546) in Human Reference Genome hg19. The OCAv3 NGS Assay is a laboratory developed test designed to find gene mutations within tumors (somatic mutations). It was not designed to find hereditary mutations. Only DNA is analyzed in this application; RNA analysis is not performed.

Analytical Sensitivity and Specificity: The OCAv3 NGS Assay has been determined to be suitably analytically sensitive and specific for the various types of abnormalities within its reportable range, demonstrating 97.18% sensitivity compared with orthogonal assay results and 100% specificity for the mutation types reported. 99.99% or greater reproducibility has been demonstrated. All quality measures for this assay were within defined assay parameters.

15.6. APPENDIX E: MEDICATION DIARY
DOSING DIARY: KRT-232 (AMG 232) + Carfilzomib, Lenalidomide, and Dexamethasone

Subject Identification Number _____

Subject Initials _____

Investigator _____

Cycle _____

Subject Completion Instructions

This is a "diary" that you will use to keep track of when you take your oral study medications including KRT-232 (AMG 232), lenalidomide, and dexamethasone.

Please avoid food for 2 hours before and 2 hours after KRT-232 (AMG 232) study drug administration. KRT-232 (AMG 232) should be taken with a full glass (240 mL) of water. Lenalidomide and dexamethasone study drugs may be taken with or without food.

It is important that you fill out this diary every day once you take your study medications. Record the date and if tablet(s) was taken for that day. If Yes, record the time tablet(s) was taken in the next column.

You must bring this diary and all unused medication to the clinic at each visit. Therefore, it is important that you keep them in a safe place where they will not be lost.

If you have any questions about your treatment, or in case of overdose, contact your study doctor at the number below:

Investigator _____

Phone Number _____

Your assigned daily dose of KRT-232 (AMG 232) on Days 1 through Day 7 is _____ mg.

____ 15 mg tablet ____ 60 mg tablet

What if I miss a dose of KRT-232 (AMG 232)?

If you forget a dose of KRT-232 (AMG 232) and it has been less than 12 hours since your regular time, take it as soon as you remember. Otherwise, skip the missed dose. Do not take a double dose (two doses at the same time) to make up for a forgotten dose. If you vomit after taking a dose, do not repeat the dose, and you should resume dosing at the time of your next scheduled dose.

Your assigned daily dose of Lenalidomide on Days 1 through Day 21 is _____ mg.

____ 5 mg capsule ____ 10 mg capsule ____ 15 mg capsule ____ 25 mg capsule

What if I miss a dose of lenalidomide?

If you forget a dose of lenalidomide and it has been less than 12 hours since your regular time, take it as soon as you remember. Otherwise, skip the missed dose. Do not take a double dose (two doses at the same time) to make up for a forgotten dose. If you vomit after taking a dose, do not repeat the dose, and you should resume dosing at the time of your next scheduled dose.

Your assigned daily dose of oral Dexamethasone on Days 1, 8, and 15 is _____ mg. If you are receiving dexamethasone intravenously on these days with carfilzomib, you will be instructed to not take oral dexamethasone doses on these days.

____ 4 mg tablet

Your assigned daily dose of oral Dexamethasone on Day 22 is _____ mg.

____ 4 mg tablet

What if I miss a dose of dexamethasone?

If you forget a dose of dexamethasone, take it as soon as you remember it as long as your next scheduled dose is at least 72 hours away. Otherwise, skip the missed dose. Do not take a double dose (two doses at the same time) to make up for a forgotten dose. If you vomit after taking a dose, do not repeat the dose, and you should resume dosing at the time of your next scheduled dose.

Please take the specified number of tablets or capsules recorded below each study drug.

KRT-232 (AMG 232) Dosing Schedule

Day	Date (dd/mmm/yyyy)	Was dose taken? If Yes, record time taken.	Time of Dose	Number of Tablets Taken Record the number of tablets taken next to each strength.
1	__ / __ / __ __	 Yes  No	__ : __  AM  PM	15 mg 60 mg
2	__ / __ / __ __	 Yes  No	__ : __  AM  PM	15 mg 60 mg
3	__ / __ / __ __	 Yes  No	__ : __  AM  PM	15 mg 60 mg
4	__ / __ / __ __	 Yes  No	__ : __  AM  PM	15 mg 60 mg
5	__ / __ / __ __	 Yes  No	__ : __  AM  PM	15 mg 60 mg
6	__ / __ / __ __	 Yes  No	__ : __  AM  PM	15 mg 60 mg
7	__ / __ / __ __	 Yes  No	__ : __  AM  PM	15 mg 60 mg

Lenalidomide Dosing Schedule

Day	Date (dd/mmm/yyyy)	Was dose taken? If Yes, record time taken.	Time of Dose	Number of Capsules Taken Record the number of capsules taken next to each strength.
1	__ / __ / __ __	 Yes  No	__ : __  AM  PM	5 mg 10 mg 15 mg 25 mg
2	__ / __ / __ __	 Yes  No	__ : __  AM  PM	5 mg 10 mg 15 mg 25 mg
3	__ / __ / __ __	 Yes  No	__ : __  AM  PM	5 mg 10 mg 15 mg 25 mg
4	__ / __ / __ __	 Yes  No	__ : __  AM  PM	5 mg 10 mg 15 mg 25 mg
5	__ / __ / __ __	 Yes  No	__ : __  AM  PM	5 mg 10 mg 15 mg 25 mg
6	__ / __ / __ __	 Yes  No	__ : __  AM  PM	5 mg 10 mg 15 mg 25 mg
7	__ / __ / __ __	 Yes  No	__ : __  AM  PM	5 mg 10 mg 15 mg 25 mg
8	__ / __ / __ __	 Yes  No	__ : __  AM  PM	5 mg 10 mg 15 mg 25 mg
9	__ / __ / __ __	 Yes  No	__ : __  AM  PM	5 mg 10 mg 15 mg 25 mg
10	__ / __ / __ __	 Yes  No	__ : __  AM  PM	5 mg 10 mg 15 mg 25 mg
11	__ / __ / __ __	 Yes  No	__ : __  AM  PM	5 mg 10 mg 15 mg 25 mg
12	__ / __ / __ __	 Yes  No	__ : __  AM  PM	5 mg 10 mg 15 mg 25 mg
13	__ / __ / __ __	 Yes  No	__ : __  AM  PM	5 mg 10 mg 15 mg 25 mg
14	__ / __ / __ __	 Yes  No	__ : __  AM  PM	5 mg 10 mg 15 mg 25 mg
15	__ / __ / __ __	 Yes  No	__ : __  AM  PM	5 mg 10 mg 15 mg 25 mg
16	__ / __ / __ __	 Yes  No	__ : __  AM  PM	5 mg 10 mg 15 mg 25 mg

17	____/____/_____	 Yes  No	____:____  AM  PM	 5 mg  10 mg  15 mg  25 mg
18	____/____/_____	 Yes  No	____:____  AM  PM	 5 mg  10 mg  15 mg  25 mg
19	____/____/_____	 Yes  No	____:____  AM  PM	 5 mg  10 mg  15 mg  25 mg
20	____/____/_____	 Yes  No	____:____  AM  PM	 5 mg  10 mg  15 mg  25 mg
21	____/____/_____	 Yes  No	____:____  AM  PM	 5 mg  10 mg  15 mg  25 mg

Dexamethasone Dosing Schedule

Day	Date (dd/mmm/yyyy)	Was dose taken? If Yes, record time taken.	Time of Dose	Number of Tablets Taken Record the number of tablets taken next to each strength.
1*	____/____/_____	 Yes  No	____:____  AM  PM	____ 4 mg
8*	____/____/_____	 Yes  No	____:____  AM  PM	____ 4 mg
15*	____/____/_____	 Yes  No	____:____  AM  PM	____ 4 mg
22	____/____/_____	 Yes  No	____:____  AM  PM	____ 4 mg

*If you are receiving dexamethasone intravenously on these days with carfilzomib, you will be instructed to not take oral dexamethasone doses on these days.

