5.2. KRT-232 (AMG 232) Administration

KRT-232 (AMG 232) will be administered QD for 7 days every 28 days (i.e., 7 consecutive days of dosing followed by 21 consecutive days off treatment).

For QD dosing, subjects should self-administer KRT-232 (AMG 232) with or without food, with a full glass of water. KRT-232 (AMG 232) should not be crushed, chewed, or dissolved in water. Subjects should not be re-dosed with KRT-232 (AMG 232) after vomited doses.

The subject will be requested to maintain a medication diary of each dose of medication. The medication diary will be returned to clinic staff at the end of each course (APPENDIX E).

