Preparation: AMG 232 (KRT 232) uncoated tablets (LDL tablet) can be dispensed in the original container or in pharmacy dispensing bottles. **The film-coated tablets (HDL tablet) must be dispensed in the original bottle.** There are no data to support the re-packaging of HDL tablets in containers other than the original bottle.

Storage: Store intact bottles according to the drug label.

Uncoated tablet (LDL tablet):

- AMG 232 (KRT 232) 15 mg Tablets: below 25°C (77°F), protect from light.
- AMG 232 (KRT-232) 60 mg Tablets: 15°C – 30°C (59°F - 86°F), protect from light

Film-coated tablet (HDL tablet): 15°C – 30°C (59°F - 86°F), protect from light.

If a storage temperature excursion is identified, promptly return AMG 232 (KRT 232) to the proper storage temperature and quarantine the supplies. Provide a detailed report of the excursion (including documentation of temperature monitoring and duration of the excursion) to [contact] for determination of suitability.

Stability: Shelf-life stability studies of AMG 232 (KRT 232) tablets are ongoing.

Route(s) of Administration: Oral.

Method of Administration: AMG 232 (KRT 232), uncoated (LDL) or coated (HDL) tablet, can be taken with a glass of water with or without food.

Potential Drug Interactions:

AMG 232 (KRT 232) is metabolized by three uridine diphosphoglucuronosyl transferases (UGT1A1, UGT1A3, and UGT1A4) to an acyl glucuronide (M1). In vitro, M1 is not impacted by UGT1A1 polymorphic genotypes UGT1A1*1/*1, UGT1A1*1/*28 or UGT1A1*28/*28.

AMG 232 (KRT 232) is not metabolized by CYP450 isozymes. *In-vitro* study suggests that AMG 232 is a substrate for P-glycoprotein, a competitive moderate inhibitor of CYP2C8, and a time-dependent moderate inhibitor of CYP3A4. M1 is a weak inhibitor of CYP2B6. KRT-232

has the potential to cause a minor drug-drug interaction (DDI) with drugs cleared predominantly by CYP3A4 (inhibition and induction). There is no identified DDI potential for other CYP enzymes. Use caution in patients taking CYP3A4 substrates with narrow therapeutic ranges.

Since AMG 232 (KRT 232) absorption was not impacted in the presence of high pH as demonstrated in a PK simulation, KRT-232 is not likely to be affected by proton pump inhibitor-mediated increase in gastric pH.

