9.3.1.1. Collection of Specimen(s)
Blood samples (~6 mL) will be taken into K3EDTA tubes at designated time points, and immediately placed on ice. C1D1: pre KRT-232 (AMG 232), 1, 3, 5, 8, and 24 hours post (24 hr post is C1D2).

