9.3.1.2. Handling of Specimens(s)
At each time point, ~6 mL of peripheral blood will be collected in a purple-top EDTA vacutainer (Becton Dickinson Catalog # 367863 or 367899, Franklin Lakes, NJ).

Obtain venous blood by standard phlebotomy technique from a peripheral access point. NOTE: Suggest using a minimum 18G needle to avoid sample hemolysis.

Fill-up the tubes as much as possible until blood flow stops.
GENTLY invert each tube several times (8-10 times) immediately after collection to avoid sample hemolysis.
Place samples immediately **on ice** after collection; samples must be processed **within 30 minutes**.

9.3.1.3. Processing instructions:

- 1) Invert sample 8-10 times immediately before processing.
- 2) Centrifuge at 2500-3000 rpm for 10 minutes in swinging bucket (SW) or 15 minutes in a fixed angel (FA) rotor at 4°C in a refrigerated centrifuge. Make sure that the centrifuge reaches speed and is maintained throughout the entire spin.
- 3) Carefully remove tube from centrifuge.
- 4) Using a pipette, transfer equal aliquots of plasma into 2-3 labeled 2 mL cryovials, not exceeding 1.5 mL per cryovial.
- 5) Label samples as KRT-232 (AMG 232) PK, including study number (NCI10076), unique subject ID (assigned by OPEN), initials, date of collection, draw time, and time point.
- 6) Store plasma samples at -70°C or below until shipment or transfer to Johns Hopkins.

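### The patient diary restricts food around KRT-232 while Sections 5.2 and 8.1 do not, so exposure data can mix fed and fasted doses, and no food-status field appears in the documents supplied

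*Combined protocol and SAP*

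**What the plan says.** Three current texts instruct on food and KRT-232.

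- Section 5.2 (KRT-232 Administration): "subjects should self-administer KRT-232 (AMG 232) with or without food, with a full glass of water".
- Section 8.1 (Method of Administration, uncoated and coated tablets alike): the drug "can be taken with a glass of water with or without food".
- Appendix E (Medication Diary): "Please avoid food for 2 hours before and 2 hours after KRT-232 (AMG 232) study drug administration".

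The diary restriction is specific to KRT-232. The same paragraph goes on: "Lenalidomide and dexamethasone study drugs may be taken with or without food". Section 5.2 itself refers to Appendix E as the diary that subjects keep and hand back, so the diary is an operative part of the plan.

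PK is sampled around one dose only. Section 9.3.1.1 takes a pre-dose sample on Cycle 1 Day 1, then samples at 1, 3, 5, 8 and 24 hours. The only post-dose MIC-1 sample is drawn about 24 hours after that same dose (Section 9.3.2.1). Exposure-response for PD, toxicity and efficacy is a secondary objective in both parts (Sections 1.1.2 and 1.2.2). Section 13.5 compares PK parameters and MIC-1 changes across dose levels by nonparametric tests at the 0.05 level.

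**The concern.** A subject who takes KRT-232 with a meal follows Sections 5.2 and 8.1 and breaks the diary's instruction. Staff have no rule for deciding whether that is a deviation, and subjects have none for deciding which text prevails. Fed and fasted doses can therefore both occur under the plan.

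If food changes KRT-232 exposure, two uses of the data are at risk. The first is the comparison of PK parameters and MIC-1 changes across dose levels, where each escalation level holds 3 to 6 subjects (Section 13.3) and neighbouring doses are close together. The second is the link from exposure to toxicity and efficacy. It rests on one Cycle 1 Day 1 profile standing in for all seven dosing days, and that profile is less representative if the meal state on Day 1 differs from Days 2-7. No later PK profile is planned that could reveal the difference.

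**Working it through.** The plan states no figure on this point, so there is none to reproduce. The check has two parts.

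**1. Where food status could be recorded or used**

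| Place | Content | Food status? |
|---|---|---|
| Appendix E, KRT-232 table | Date, "Was dose taken? If Yes, record time taken", time, tablets by strength | No |
| PK tube label (Section 9.3.1.3) | Study number, subject ID, "initials, date of collection, draw time, and time point" | No |
| Study calendars (Sections 10.1, 10.2) | Visits, samples, diary review | No |
| PK analysis set (Section 13.1.6) | Any dose plus measurable concentrations | No |
| PK/PD analysis (Section 13.5) | By dose and time, compared across dose levels | No |
| PK sample collection form (Section 9.3.1.4) | Mentioned, not reproduced | Cannot be checked |

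**2. Illustrative size if food matters**

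The documents give the escalation doses: 60, 90, 120, 180 and 240 mg (Section 5.4). The steps are 90/60 = 1.50, 120/90 = 1.33, 180/120 = 1.50 and 240/180 = 1.33. Section 2.7.2 describes exposure as dose proportional over the proposed range, so a fed/fasted AUC ratio of 1.33 to 1.5 would equal a whole dose step.

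The following inputs are assumptions, because the documents supply none of them: the between-subject AUC coefficient of variation (CV), the fed/fasted AUC ratio R, and the fed share f.

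For a two-group log-normal mixture:

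- Total log-variance = ln(1 + CV²) + f(1 − f)(ln R)²
- Relative increase = f(1 − f)(ln R)² / ln(1 + CV²)

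With CV = 40%, ln(1 + 0.16) = 0.148. For f = 0.5, f(1 − f) = 0.25. For f = 0.1, f(1 − f) = 0.09.

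| R | (ln R)² | Increase, half fed | Increase, 10% fed |
|---|---|---|---|
| 1.0 | 0 | 0% | 0% |
| 1.2 | 0.033 | 0.0083/0.148 = 6% | 0.0030/0.148 = 2% |
| 1.5 | 0.164 | 0.0411/0.148 = 28% | 0.0148/0.148 = 10% |
| 2.0 | 0.480 | 0.1201/0.148 = 81% | 0.0432/0.148 = 29% |

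An even split maximises f(1 − f), so the half-fed column is the upper end for each ratio.

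The assumed CV also matters. With half the subjects fed, a base CV of 30% becomes 32.2%, 36.8% and 47.9% for R = 1.25, 1.5 and 2.0. A base CV of 50% becomes 51.5%, 55.0% and 64.0%.

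Food can also line up with dose by chance. With half the subjects fed, all members of a three-subject cohort share one food state with probability 2 × 0.5³ = 25%.

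**The case against.** The strongest reply is that the texts can all be obeyed together. Sections 5.2 and 8.1 grant a permission and the diary adds a restriction, so a subject who fasts satisfies all three. A reader might infer that the instructions are opposite, but they are not. What stands is that a fed dose satisfies two of the texts and breaches the third.

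A reader might also infer that the exposure data do mix fed and fasted doses, or that staff instructions govern Cycle 1 Day 1 while the diary governs later doses. The documents show neither. They do not say that any subject is dosed fed. The calendars show diaries dispensed or reviewed from Cycle 1 Day 1, and the diary has a Day 1 row.

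Nor can it be said that food status goes unrecorded. The PK sample collection form and the case report forms for dosing are not reproduced, and one of them may carry the field.

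It is also tempting to ask for a food covariate in the MIC-1 analysis. That does not follow. MIC-1 is drawn after the same dose as the PK profile, so measured Cmax and AUC already carry any food effect and are correctly paired with the MIC-1 response. Wider exposure spread does not by itself weaken that relationship. What remains is the comparison by dose level and how well Day 1 represents Days 2-7.

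Finally, the size rests wholly on assumptions. The permission in Section 8.1 is compatible with no food effect. Parts of the human PK text are redacted, so the lack of a food-effect figure does not show that the sponsor has none. The dose-escalation decisions in Sections 5.4 and 5.6 do not use PK, so the MTD determination does not depend on this point. These limits narrow the consequence but leave the textual conflict in place.

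**Conclusion.** The conflict is wrong as written: the diary is stricter than Sections 5.2 and 8.1, and nothing says which prevails. It should be corrected whether or not food affects exposure.

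The statistical consequence is conditional. Exposure data can mix fed and fasted dosing, and nothing in the documents supplied would let an analyst separate them, subject to the unseen PK form. Under an assumed 40% CV, the increase in log-AUC variance runs from zero with no food effect to 81% at a twofold effect with half the subjects fed. With 10% fed, the same twofold effect gives about 29%. A ratio of 1.33 to 1.5 would match a planned dose step. The loss, if any, falls on the comparisons across dose levels and on using Day 1 exposure for the toxicity and efficacy relationships.

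**What to change.** Reconcile Section 5.2, Section 8.1 and Appendix E to one food instruction for KRT-232. Which instruction that should be is for the clinical team.

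Check whether the PK sample collection form already captures food status at the Cycle 1 Day 1 PK dose. If it does not, add one field there or on the case report form, and state in Section 13.5 that PK comparisons across dose levels will be described by food status. Description is enough, since 3 to 6 subjects per level give little room for adjustment.

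The cost is a wording change in the diary or the protocol body and, at most, one data field. Food status not captured at dosing cannot be reliably recovered later.
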